#### 1. OBJECTIVES

# 1.1 Primary Objectives

The primary objectives of this study are to determine the safety, tolerability and clinical activity of telaglenastat (CB-839) in combination with azacitidine (AZA) for patients with advanced MDS.

# 1.2 Secondary Objectives

The secondary objectives of the study are:

- 1.2.1. To explore the pharmacokinetics (PK) of telaglenastat in combination with AZA
- 1.2.2. To explore the pharmacodynamics (PDn) of telaglenastat in combination with AZA
- 1.2.3. To assess overall survival, event-free survival and duration of response of telaglenastat in combination with AZA

NCT ID: NCT03047993

Protocol 2016-0636 Date: 06/03/2019

Page **4** of **39** 

#### 2. BACKGROUND AND SCIENTIFIC RATIONALE

## 2.1 Background

Myelodysplastic syndromes (MDS) are malignant clonal disorders characterized by ineffective hematopoiesis, bone marrow dysplasia, peripheral cytopenias including thrombocytopenia, and a propensity to transform into acute myeloid leukemia (AML).(1, 2) Classically, MDS is associated with apoptosis and excessive proliferation, resulting in a paradoxical combination of a hyper-cellular marrow and peripheral cytopenias.(3) The incidence of MDS in the United States is rising, with approximately 20,000 to 30,000 new cases of MDS diagnosed annually, and a median age at diagnosis of 70 years.(3, 4)

Over the past decade, clinical use of the hypomethylating agent azacitidine has been shown to improve patient quality of life, decrease transfusion requirements, and improve outcome parameters in MDS patients, and is now a standard of care for MDS patients requiring therapy. With current HMA regimens, achievement of an ORR is estimated at 28-70%, with a CR rate of only 6-34% in patients with MDS treated with front-line HMA therapy, and with a median length of response in the HMA-responders of only 8 to 10 months.(5-10)

MDS patients requiring therapy include those with intermediate-2 or High-risk disease by IPSS, or high or very-high risk by R-IPSS.(11) In addition, patients with otherwise intermediate MDS with high-risk molecular features including *TP53*, *ASXL1*, *EZH2*, and/or *RUNX1* mutations have been identified as a subgroup that may benefit from early therapeutic intervention.(12)

#### 2.2 Rationale for Glutaminase Inhibition:

Tumor cells including MDS cells exhibit an altered metabolic profile compared with normal cells, presumed to favor rapid growth and proliferation as well as augmented survival in hypoxic environment. As first noted by Warburg in 1924, tumor cells display "aerobic glycolysis" in lieu of oxidative phosphorylation, and thereby generate limited ATP from glucose. Consequently, many tumor cells require a continuous supply of exogenous glutamine (GLN) that is used to fuel the tricarboxylic acid (TCA) cycle for the generation of ATP and as a precursor in the generation of amino acids, nucleic acids, and fatty acids. This enhanced utilization of GLN requires the activity of glutaminase, a mitochondrial enzyme which converts GLN to glutamate (GLU). GLU, in turn, has a number of important bioenergetic and biosynthetic functions including as an anaplerotic intermediate fueling the TCA cycle via conversion to  $\alpha$ -ketoglutarate ( $\alpha$ KG). Many tumors have been found to have a pronounced upregulation of glutaminase. These tumors are sensitive to withdrawl of GLN from growth medium, usually have a high cellular ratio of GLU to GLN, and are very sensitive to the inhibition of glutaminase by telaglenastat .

Protocol 2016-0636 Date: 06/03/2019

Page **5** of **39** 

Anti-tumor activity of glutaminase knock-down with shRNA or inhibition with small molecules has been reported both *in vitro* and *in vivo*.(13, 14) Mutations in the TCA cycle enzyme isocitrate dehydrogenase (IDH), either in the cytoplasm (IDH1) or mitochondria (IDH2), have been identified in both AML and MDS. These mutations result in conversion of the TCA cycle intermediate aKG into 2-hydroxyglutarate (2HG). 2HG, considered an oncometabolite, accumulates in the cell resulting in dioxygenase blockade, DNA and histone hypermethylation, and ultimately, impaired cell differentiation.

[figure not shown]

Figure 1: Metabolic pathway associated with IDH1 and IDH2 mutations.

Telaglenastat is a potent and selective reversible inhibitor of glutaminase activity. Two alternative splice variants of glutaminase (GLS), GAC and KGA, are found in tumors and in normal tissues including lung, liver, heart, kidney, spleen, intestine and brain. A separate gene encodes glutaminase-2 (GLS2), found mainly in the liver. Telaglenastat is an allosteric and noncompetitive inhibitor of both GAC and KGA isoforms of glutaminase, but does not inhibit GLS2. Incubation of recombinant human glutaminase with CB-839 results in time-dependent and slowly reversible inhibition of glutaminase activity (IC50 = 34 nM with 1 hour pre-incubation). Glutaminase inhibition is associated with antiproliferative activity in a wide range of tumor cell lines. Pro-apoptotic activity

[figure not shown]
Protocol 2016-0636 Date: 06/03/2019

Page **6** of **39** 

has been observed in triple-negative breast cancer (TNBC), multiple myeloma, mesothelioma, and many additional solid and hematologic tumors.

Recent experimental data suggest that glutamine metabolism is very important for leukemic blasts. Removal of glutamine from the culture media of AML cell lines inhibits mTORC1 and induces apoptosis, and shRNA knockdown of SLC1A5, a high-affinity transporter for GLN, inhibits tumor formation in mouse AML xenografts. Leukemic cells may be dependent on glutamine utilization pathways to provide carbon skeletons for TCA activity (Matre et al, ASH 2013).

The antiproliferative and pro-apoptotic effect of telaglenastat has been evaluated alone and in combination with the hypomethylating agent azacitidine in two different AML cell lines (data from OCI-AML3 cell line shown in Figure 2). Both telaglenastat and azacitidine showed significant antiproliferative effects in both cell lines. In combination, substantially greater inhibition of cell number and induction of apoptosis was observed. The mechanism whereby these agents act together has not been fully established. However, recent findings indicate that telaglenastat significantly depletes the cellular pool of aspartate, which is a substrate for the synthesis of purine and pyrimidine nucleotides. In multiple myeloma cells, telaglenastat caused a significant depletion of intracellular pools of aspartate, adenylosuccinate and total adenylate. Azacitidine is a prodrug that is metabolized to 5-aza-2'-deoxycytidine-triphosphate, which is incorporated into DNA and result in DNA damage (Stresemann C and Lyko F, Int. J. Cancer 123:8-13 (2008). The combination of nucleotide depletion and induction of DNA damage may result in enhanced impairment of DNA replication.

**Figure 2:** Anti-proliferative and pro-apoptotic effects of Telaglenastat and azacitidine in AML cell line in vitro. OCI-AML3 cells were incubated with increasing concentrations of

Protocol 2016-0636 Date: 06/03/2019

Page **7** of **39** 

Telaglenastat, azacitidine, or Telaglenastat + azacitidine for 5 days. The antiproliferative effect of single agent or combination treatment was determined by cell counting. The induction of apoptosis was determined by staining with Annexin V. This work was carried out in the laboratory of [name] at MD Anderson Cancer Center.

## 2.3 In Vivo Pharmacodynamics of telaglenastat :

Telaglenastat inhibition of cellular glutaminase activity has been assessed in rodents. These studies have demonstrated that oral administration of Telaglenastat results in a rapid, dose-dependent inhibition of glutaminase in mice bearing established human tumor xenografts. Moreover, all tissues examined with the exception of brain (where there is limited exposure) and liver (where GLS2 predominates) showed evidence of glutaminase inhibition, although less dramatic than in tumors.

When telaglenastat was administered to immunocompromised mice bearing established human TNBC and myeloma xenografts, there was a significant inhibition of tumor growth, both as a single agent and in combination with standard of care chemotherapeutics. Telaglenastat administration was well-tolerated up to 400mg/kg BID and resulted in substantial inhibition of tumor growth.

# 2.4 PK and PD of telaglenastat in Tumors and Tissues in Mice

The tissue distribution and PD response to CB-839 was evaluated in mice bearing the human TNBC tumor HCC1806 by measurement of drug concentration and glutaminase inhibition, respectively. Telaglenastat was administered as a 200 mg/kg single oral dose to female SCID/bg mice. Excellent exposure to telaglenastat was observed in plasma, in the tumor, and in all other tissues examined except brain, where exposure was 20-fold lower than in plasma. GLN concentration increased, while GLU and ASP decreased substantially in tumors relative to untreated controls. GLU and ASP remained essentially unchanged in non-tumor tissues, suggesting that despite significant exposure to telaglenastat, inhibition of glutaminase does not result in product depletion in normal tissues. Other metabolic pathways appear to resupply the intracellular pools of GLU in non-tumor tissues with the exception of the spleen.

#### 2.5 Nonclinical Metabolism and Pharmacokinetics:

Please refer to the Investigator's Brochure (IB) for a more detailed description of the nonclinical metabolism and PK.

Systemic exposure to telaglenastat following oral administration is highly species dependent due to significant cross-species differences in absorption and metabolism.

Protocol 2016-0636 Date: 06/03/2019

Page **8** of **39** 

Based on the *in vitro* and *in vivo* ADME data, good oral exposure of telaglenastat in humans is predicted.

The oral exposure in female rats was found to be higher than in male rats because of more extensive metabolism in male rats. *In vitro* studies also showed more rapid metabolism of telaglenastat in male rat liver microsomes and hepatocytes than in female, whereas no differences were observed *in vitro* using human hepatocytes. Oral exposure of telaglenastat in rats was also affected by feeding status. Systemic exposure to telaglenastat was higher in fasted rats than in fed rats following oral administration.

## 2.5.1 Absorption

The apical-to-basolateral permeability of telaglenastat in human Caco-2 monolayers was determined to be 9.6 x 10^-6 cm/s and is predictive of good absorption in humans. The oral bioavailability of 44-70% in mice and 66-157% in rats demonstrated good absorption of telaglenastat in these species.

#### 2.5.2. Distribution:

High *in vitro* plasma protein binding of telaglenastat was observed in mouse, rat, dog, and human plasma using an ultracentrifugation approach. The mean plasma protein binding was 98.0, 97.0, 97.9, and 99.1%, respectively. As described in Section 2.4, following a single oral dose of 200 mg/kg to SCID/bg mice, telaglenastat was broadly distributed to tissues including heart, lung, spleen, muscle, and subcutaneously-implanted tumors; brain had 20-fold lower telaglenastat levels.

#### 2.5.3. Metabolism:

In vitro metabolic stability of telaglenastat was evaluated using cryopreserved hepatocytes derived from mice, rats, dogs, monkeys (cynomolgus, rhesus, and marmoset), and humans. Telaglenastat was most stable in human hepatocytes. Gender differences were observed only in rats; CB-839 was more stable in rat hepatocytes from females. The *in vitro* clearance derived from the hepatocyte stability is well correlated with *in vivo* clearance in mice, rats, dogs, marmoset monkeys, and cynomolgus monkeys.

Two pathways of metabolic transformation of telaglenastat have been identified *in vitro* in hepatocytes and *in vivo*: amide hydrolysis and P450-mediated hydroxylation. There are considerable differences in the mechanism of metabolism across species. All metabolites resulting from amide hydrolysis and hydroxylation of CB-839 have a low abundance (<10%) in human hepatocyte incubations up to 4 hr. Significant exposure of the human metabolites identified thus far is anticipated in the non-clinical GLP toxicity studies.

#### 2.5.4. Excretion:

NCT ID: NCT03047993 Protocol 2016-063 Date: 06/03/2019

Page **9** of **39** 

About 0.3-1.2% of orally dose CB-839 was eliminated via biliary excretion in bile duct-cannulated rats. And biliary excretion happened predominately in the first 2 hr after dosing. On the other hand, when CB-839 was dosed orally to bile duct-cannulated rats, 41 to 49 reduction in systemic exposure to CB-839 was seen relative to normal rats, suggesting a significant amount of CB-839 is flowing through the bile, and perhaps undergoing enterohepatic recirculation in normal animals. Further studies are needed to better understand biliary excretion of CB-839 in rats.

### 2.5.5. Drug-drug interaction

Direct and time-dependent inhibition (TDI) of human cytochrome P450 (CYP) enzymes by telaglenastat was evaluated in human liver microsomes (HLM). CB-839 was not an inhibitor for CYP1A2, CYP2B6, CYP2C8, CYP2C19, CYP2D6 and CYP3A. CB-839 appears to be an inhibitor of CYP2C9 with an IC50 of 1.8 - 6.7  $\mu$ M. Further studies are needed to understand the time-dependency of inhibition. Telaglenastat was not an inducer of human CYP1A2, 2B6, or 3A4 in cryopreserved hepatocytes from three donors. Telaglenastat is a moderate substrate of efflux transporters with an efflux ratio of 6.2 in Caco-2 monolayers.

## 2.6 Genotoxicity

The genotoxicity of telaglenastat in bacteria was evaluated in a GLP-compliant Ames test. There were no findings of mutagenicity of telaglenastat.

#### 2.7 Clinical Data

The safety, pharmacokinetics (PK), and pharmacodynamics (PDn) following oral administration of telaglenastat is being evaluated in three ongoing Phase 1 clinical trials in CX-839-001 (solid tumors), CX-839-002 (MM and NHL), and CX-839-003 (acute leukemia). Increasing doses of telaglenastat resulted in an increase in plasma concentration of telaglenastat and in inhibition of glutaminase activity in platelets and in tumors. As of January 26, 2016, 147 subjects have been treated with telaglenastat monotherapy across the 3 studies, at doses of 100 – 1000 mg orally TID fasted, or 600 - 1000 mg BID orally with food. To date, 2 DLT events (elevated creatinine and elevated LFTs) have been reported for the monotherapy. Although a maximum tolerated dose (MTD) has not been defined, 800 mg BID is the highest dose that is confirmed to be safe and well tolerated as monotherapy. The most frequent drugrelated grade 3-4 toxicity has been reversible elevations in liver function tests, primarily ALT, AST and GGT, although the frequency of Grade 3/4 LFT elevations is substantially reduced with BID dosing with food as compared to the original TID regimen. CB-839 has been evaluated at doses up to 1000 mg TID in patients with hematologic malignancies.

Protocol 2016-0636 Date: 06/03/2019

Page **10** of **39** 

In the CX-839-003 study the safety and tolerability of telaglenastat is being evaluated in patients with hematological malignancies (acute myelogenous leukemia (AML), acute lymphocytic leukemia (ALL), or myelodysplastic syndrome (MDS) either as monotherapy or in combination with azacitidine. A total of 11 leukemia patients have received telaglenastat as monotherapy on the BID schedule with food and treatment related AEs are presented in TABLE 1. Overall, 81.8% of patients experienced an AE that was considered at least possibly related to CB-839. The most frequent CB-839-related AEs were hematological (thrombocytopenia and anemia) with other AEs including Grade 1/2 elevated AST, elevated creatinine, constipation and dyspnea. The hematological AEs were all Grade 3/4 whereas the non-hematological AEs were typically mild to moderate in intensity (Grade 1/2), reversible and manageable without dose interruption or modification. No Grade 3/4 elevations in LFTs were noted. CB-839-related Grade 3/4 events included thrombocytopenia (4), neutropenia (2), anemia (2), lymphopenia (1), hyponatremia (1) and stomatitis (1).

Table 1: CX-839-003 Treatment-Related Adverse Events in ≥ 2 patients - BID fed

BID Monotherapy (N=11)			
MedDRA Preferred Term		Number (%) of patients	
Medbix Freiened Teini	All Grades	≥Grade 3	
Patients with Any CB-839-Related AE	9 (81.8)	5 (45.5)	
THROMBOCYTOPENIA	4 (36.4)	4 (36.4)	
ASPARTATE AMINOTRANSFERASE INCREASED	2 (18.2)	0	
BLOOD CREATININE INCREASED	2 (18.2)	0	
CONSTIPATION	2 (18.2)	0	
DYSPNOEA	2 (18.2)	0	
NEUTROPENIA	2 (18.2)	2 (18.2)	

Reductions in blast counts were achieved in 2 patients with AML receiving monotherapy telaglenastat including one with CRi.

NCT ID: NCT03047993 Protocol 2016-0636 ate: 06/03/2019

Version 1

Page **11** of **39** 

On the CX-839-003 study telaglenastat also is being evaluated at escalating doses (400 mg BID – 800 mg BID) in combination with standard dose azacitidine (75 mg/m^2 dosed IV or SC for 7 days of every 28-day cycle). As of the data cutoff for this document 4 patients have received telaglenastat in the 400 mg BID dose cohort in combination with azacitidine One of 4 patients has experienced a treatment-related AE considered at least possibly related to telaglenastat. To date, no DLTs have occurred. Efficacy data are not yet available for patients receiving telaglenastat in combination with azacitadine.

#### 3. STUDY ELIGIBILITY

#### 3.1 Inclusion Criteria

- 1. Signed, informed consent must be obtained prior to any study specific procedures.
- 2. Subjects must be ≥ 18 years of age at the time of informed consent
- 3. Subjects with a histologically confirmed diagnosis of MDS, including both MDS and RAEB-T (AML with 20-30% blasts and multilineage dysplasia by FAB criteria) by World Health Organization (WHO) and chronic myelomonocytic leukemia (CMML) are eligible.
- 4. Subjects with high-risk MDS (i.e. IPSS Intermediate-2 or high-risk; or R-IPSS high or very-high risk). Patients with Intermediate-1 risk by IPSS or Intermediate risk by R-IPSS and with IDH1 or IDH2, or high-risk molecular features including TP53, ASXL1, EZH2, and/or RUNX1 mutations are also eligible.
- 5. Subjects with prior hypomethylating agent therapy exposure may be eligible based on discussion with the PI.
- 6. Eastern Cooperative Oncology Group (ECOG) Performance Status of 0-2.
- 7. Adequate liver function, as evidenced by a serum bilirubin < 2x the ULN (except for patients with Gilbert's disease) and ALT or AST < 3x the laboratory ULN.
- 8. Adequate renal function including creatinine clearance > 30 mL/min based on the Cockcroft-Gault equation.
- Able to understand and voluntarily sign a written informed consent, and willing and able to comply with protocol requirements.
- 10. Resolution of all clinically significant treatment-related, non-hematological toxicities, except alopecia, from any previous cancer therapy to < Grade 1 prior to the first dose of study treatment

Protocol 2016-0636 ate: 06/03/2019

Page **12** of **39** 

11. Female patients of childbearing potential must have a negative serum or urine pregnancy test within 3 days of the first dose of study drug and agree to use dual methods of contraception during the study and for a minimum of 3 months following the last dose of study drug. Post-menopausal females (> 45 years old and without menses for > 1 year) and surgically sterilized females are exempt from these requirements. Male patients must use an effective barrier method of contraception during the study and for a minimum of 3 months following the last dose of study drug if sexually active with a female of childbearing potential.

#### 3.2 Exclusion Criteria:

- 1. Any prior or coexisting medical condition that in the investigator's judgment will substantially increase the risk associated with the subject's participation in the study.
- 2. Psychiatric disorders or altered mental status precluding understanding of the informed consent process and/or completion of the necessary study procedures
- 3. Active uncontrolled infection at study enrollment including known diagnosis of human immunodeficiency virus or chronic active Hepatitis B or C infection.
- 4. Clinically significant gastrointestinal conditions or disorders that may interfere with study drug absorption, including prior gastrectomy.
- 5. Patients with known active CNS disease, including leptomeningeal involvement.
- 6. Impaired cardiac function, uncontrolled cardiac arrhythmia, or clinically significant cardiac disease including the following: a) New York Heart Association Grade III or IV congestive heart failure, b) myocardial infarction within the last 6 months
- 7. Subjects with a QTc > 480 ms (QTc > 510 msec for subjects with a bundle branch block at baseline).
- 8. Nursing or pregnant women.
- 9. Subjects with known hypersensitivity to study drugs or their excipients.

#### 4. TREATMENT PLAN

# 4.1 Study Design

NCT ID: NCT03047993 Protocol 2016-0636 ate: 06/03/2019

Page **13** of **39** 

This is a Phase 1b/II clinical trial designed to assess the safety, tolerability and efficacy of telaglenastat in combination with AZA for the treatment of advanced MDS. Patients will be treated with standard AZA (IV or SQ 75mg/m2 IV daily x 7 days) and telaglenastat orally twice daily continuously for 28 days per treatment cycle. A cycle will consist of 28 days of dosing. Patients will continue on study therapy unless they have evidence of progressive disease or unacceptable toxicity. Other objectives include exploring the PK and PDn of telaglenastat in combination with AZA.

#### 4.1.1. Phase 1b:

In the Phase 1b portion, telaglenastat will be administered at the goal starting dose level 0 of 600mg BID continuously. The MTD is defined as the highest dose level with </= 1 out of 6 patients experiencing a DLT during the first cycle.

The first 6 patients will be treated at dose level 0. If </= 1 out of the 6 patients experience a DLT during the first cycle, this level will be identified as the RP2D and the study will progress to the Phase II portion. If > 2 out of the 6 patients experience a DLT during the first cycle, this dose level would exceed the MTD, and an additional 6 patients will be treated at the next lower dose level. Reduced dose level -1 is defined in Table 1 below. Patients treated in the Phase 1b portion that are removed from study before day 28 for any reason other than toxicity, and have not experienced DLT, will be replaced.

AZA will be administered subcutaneously (SQ) or intravenously (IV) for 7 days of every cycle (days 1-7) as determined by the treating physician. Both SQ and IV forms of administration are FDA-approved and are considered interchangeable, based on patient and physician preference.

Table 1: Dose de-escalation for telaglenastat and AZA

Dose Level	CB-839 (oral)	AZA (IV or SQ)
0	600 mg BID days 1-28	75 mg/m2 days 1-7
-1	400 mg BID days 1-28	75 mg/m2 days 1-7

Dose reductions beyond those mentioned in this table or different to the doses specified should be discussed with the PI and documentation of the justification recorded in the medical record.

#### 4.1.1.2. Dose De-escalation Procedures:

A dose-limiting toxicity (DLT) is defined as any Grade 3 or higher non-hematologic adverse event or abnormal laboratory value occurring during the first cycle (i.e. the first 28 days) on study except those that are clearly and incontrovertibly due to disease progression or extraneous causes, with the following exceptions:

Protocol 2016-0636 ate: 06/03/2019

Page **14** of **39** 

 CTCAE v4.03 Grade 3 AST or ALT that resolves to < Grade 2 within 14 days
 without an associated rise in bilirubin

- Grade 3 nausea, vomiting or diarrhea that can be managed to < Grade 2 with
 standard antiemetic or antidiarrheal medications
- Grade > 3 electrolyte abnormality that lasts < 24 to 72 hours, is not clinically complicated, and resolves spontaneously or responds to conventional medical interventions
- Grade 3 biochemical abnormalities of amylase or lipase without clinical evidence of pancreatitis

Hematologic DLT is defined as Grade > 3 neutropenia and/or thrombocytopenia with a hypocellular bone marrow lasting for 6 weeks or more after the start of a course in the absence of underlying MDS. Anemia will not be considered for the definition of DLT.

**4.1.1.3**. The first 6 patients will be treated at dose level 0. If DLT occurs in > 2/6 evaluable patients, this dose level would exceed the MTD, and an additional 6 patients will be treated at the lower dose level. The highest dose level at which 0-1/6 patients experience DLT will be used as the RP2D. Should >2/6 DLTs occur in dose level -1, the combination may be considered too toxic in this indication and the study may be discontinued.

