#### 7.7 IND Summaries:

A Toxicity Summary will be submitted to the IND Office Medical Monitor after the first six evaluable patients complete cycle one of study treatment, prior to the Dose modification or Phase II.

A Toxicity Summary will be submitted to the IND Office Medical Monitor after the first 7 evaluable patients and every 7 evaluable patients thereafter.

A Response Summary will be submitted to the IND Office Medical Monitor after 16 evaluable patients complete 6 cycles of study treatment.

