#### 8.1.1 Phase lb:

The Phase Ib part of the study is performed to assess the safety of telaglenastat in combination with AZA. We will first enroll 6 patients at dose level 0. If only 0 or 1 of 6 patients experiences a DLT, the dose level will be identified as the RP2D. If at least 2 of 6 patients experience DLTs, then the MTD has been exceeded and 6 patients will be treated at the lower dose level (i.e. dose level -1). If at least 2 of 6 patients experience DLTs in dose level -1, the combination may be considered too toxic in this indication and the study may be discontinued. The 6 patients treated at the RP2D level will be evaluated in the Phase II portion. A maximum of 12 patients will be enrolled in the Phase 1b part of the study.

A Toxicity Summary will be submitted to the IND Office Medical Monitor after the first six evaluable patients complete cycle one of study treatment, prior to the Dose modification or Phase II.

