### **8.1.3. Toxicity:**

The method of Thall, Simon and Estey will be used for toxicity monitoring for the Phase II part of this study.(16) For monitoring purposes, toxicity is defined as DLT which occurs during the first cycle. Denote the probability of toxicity by  $P_T$ . We assume as a priori,  $P_T \sim$  beta (0.6, 1.4). Our stopping rule is to stop the trial if  $Pr(P_T > 0.30 \mid data) > 0.90$ . That is, we will stop the trial for new patient enrollment if at any time during the study; we determine that there is more than 90% chance that the toxicity rate is more than 30%. This toxicity stopping rule will be applied in cohort size of 7, starting from the 7th patient. Stopping boundaries corresponding to this stopping rule are listed in Table 1. The operating characteristics are summarized in Table 2. The design software Multc Lean Desktop (version 2.1) developed by the Department of Biostatistics at M. D. Anderson Cancer Center (MDACC) was used to generate the toxicity stopping boundaries and the operating characteristics table.

Table 1. Early stopping boundaries for toxicity monitoring

# of patients ( in cohort size of 7, starting from the 7 th patient)	Stop the trial if there are this many patients with toxicities:
7	4-7
14	7-14
21	10-21

Table 2. Operating characteristics for toxicity monitoring

True toxicity rate	Prob(stop the trial early)	Average sample size
0.10	0.0028	27.94
0.20	0.0398	27.22
0.30	0.1817	24.69
0.40	0.4639	19.91
0.50	0.7697	14.37

NCT ID: NCT03047993

Protocol 2016-0636 ate: 06/03/2019

Page **35** of **39** 

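### A hematologic DLT takes six weeks to establish, but the dose rule in 4.1.1 and the Phase II stopping rule in 8.1.3 count only first-cycle DLTs, and no decision is told to wait

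*Combined protocol and SAP*

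**What the plan says.** All references are to the combined protocol and SAP.

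- **Definition.** Section 4.1.1.2 has two DLT sentences. The non-hematologic one covers events "occurring during the first cycle (i.e. the first 28 days) on study". The hematologic one has its own clock: cytopenia with a hypocellular marrow "lasting for 6 weeks or more after the start of a course in the absence of underlying MDS".
- **Dose rule.** Section 4.1.1 defines the MTD, and the step to Phase II, by the number of six patients "experiencing a DLT during the first cycle". Section 4.1.1.3 gives the rule without a cycle limit: "The highest dose level at which 0-1/6 patients experience DLT will be used as the RP2D". Section 8.1.1 also omits the limit.
- **Phase II stopping rule.** Section 8.1.3 says "toxicity is defined as DLT which occurs during the first cycle". No other section defines the event for this rule.
- **Timing of the decision.** Sections 7.7 and 8.1.1 call for a toxicity summary "after the first six evaluable patients complete cycle one of study treatment" and "prior to the Dose modification or Phase II".
- **Cycle length.** Section 4.1: "A cycle will consist of 28 days of dosing". Section 4.2.3 allows 5 days either way, or resolution of a drug-related event, taking the earlier. Section 4.5 lets cycle 2 wait for count recovery.

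**The concern.** The plan chose to treat prolonged marrow aplasia as dose-limiting. Its two formal safety rules then use a window that closes before such an event can be confirmed. A patient with aplasia from cycle 1 could be tallied as free of DLT in the six-patient decision and at the Phase II looks.

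Hematologic toxicity matters for this drug. Section 2.7 reports that, among 11 leukemia-study patients on twice-daily monotherapy, related thrombocytopenia of Grade 3 or higher occurred in 4 and neutropenia in 2. Neither duration nor marrow findings are given, so these counts do not estimate the aplasia rate. They show only why the event should be countable.

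**Working it through.** **1. Timing.** Six weeks is 42 days. The shortfall against a 28-day cycle is 42 − 28 = 14 days. Against the longest cycle under 4.2.3 (28 + 5 = 33 days) it is 42 − 33 = 9 days. Section 4.5 may delay cycle 2 further, but does not say whether cycle 1 is still running meanwhile.

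**2. The plan's own figures.** With the beta(0.6, 1.4) prior and the 0.90 threshold of 8.1.3, the posterior probability that the toxicity rate exceeds 0.30 is 0.9014 at 4/7, 0.9245 at 7/14 and 0.9443 at 10/21. With one event fewer it is 0.717, 0.818 and 0.876. The boundaries are therefore right. An exact binomial recursion over looks at 7, 14 and 21 (maximum 28) gives stopping probabilities of 0.0028, 0.0398, 0.1817, 0.4639 and 0.7697 at true rates of 0.1 to 0.5, matching Table 2 of that section. The issue is which events enter the count.

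**3. Effect on the rules (illustration).** All rates here are assumptions. Let the non-hematologic DLT rate be 10%, let *h* be an independent rate of prolonged aplasia, and let *s* be the share of aplasia events newly counted. The rest are explained by persistent MDS or are already DLTs through infection or bleeding. Then

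p = 1 − 0.9 × (1 − s·h), and P(0 or 1 DLT in 6) = (1 − p)^6 + 6p(1 − p)^5.

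With none counted, p = 0.10 and the result is 0.5314 + 0.3543 = 0.886. With h = 0.10 and s = 0.5, p = 1 − 0.9 × 0.95 = 0.145 and the result is 0.3907 + 0.3975 = 0.788.

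| Share counted (s) | P(0–1 of 6) at h = 5% / 10% / 20% | P(Phase II rule stops) at h = 5% / 10% / 20% |
|---|---|---|
| 0 | 0.886 throughout | 0.003 throughout |
| 0.25 | 0.863 / 0.839 / 0.788 | 0.004 / 0.006 / 0.012 |
| 0.5 | 0.839 / 0.788 / 0.680 | 0.006 / 0.012 / 0.033 |
| 1 (upper bound) | 0.788 / 0.680 / 0.464 | 0.012 / 0.033 / 0.142 |

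With h = 10% and a non-hematologic rate of 5%, P(0–1 of 6) is 0.967 with none counted, 0.891 with half and 0.788 with all. At 15% it is 0.776, 0.674 and 0.570.

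**4. If later events do count for the RP2D.** Then only patients short of day 42 are missed when the sixth reaches day 28. With even accrual of *a* per month, entries are 30.4/a days apart. The number short of day 42 is 1 of 6 at 1 or 2 per month, 2 of 6 at 3 or 4, and 3 of 6 at 6. The accrual rates are assumptions.

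**5. Replacement.** Section 8.2.2 requires 85% of 56 planned telaglenastat doses, which is 47.6. Missing 9 leaves 47/56 = 83.9%, so the patient is non-evaluable. The exemption covers doses missed because of a DLT, and a hold for low counts is not yet a DLT before day 42. Section 4.5 leaves such holds to the investigator.

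**6. Data at day 42.** If cycle 2 starts on time, the scheduled blood counts under 5.2.4 fall at C2D1 (day 29) and C3D1 (about day 57). Marrows fall at C2D1 and C4D1 (about day 85). No scheduled visit tests the six-week criterion when it falls due.

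**The case against.** The best defence is that the hematologic sentence has its own clock, tied to the course that caused the event. Dating it to cycle 1 by onset is natural and makes the definition work. The 28-day gloss sits in the non-hematologic sentence, and 4.1.1.3 and 8.1.1 have no cycle limit. This stands as a sensible intention, but no text states it, and 8.1.3 carries the limit.

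Other cover is real. Section 4.1.2 bases the RP2D on all the clinical data. The Medical Monitor receives toxicity summaries. Infection or bleeding of Grade 3 or higher in cycle 1 can count as a non-hematologic DLT. The count-recovery rule in 4.5 should delay cycle 2 for many of the patients concerned, since its exception is for residual disease. For patients taken off study early, 4.1.1 does not replace those removed for toxicity. None of these puts the event into the formal counts.

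Several stronger readings are tempting but unsupported:

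- *The summary is due at day 28.* The wording sets an order (after cycle one, before dose change or Phase II), not a deadline. Waiting is allowed, though not required.
- *No hematologic DLT can ever count toward the RP2D.* The sections conflict on this; they do not settle it that way.
- *The clause on underlying MDS excludes everyone in an MDS trial.* It more probably means no persistent MDS in that marrow.
- *The monotherapy counts show an aplasia risk.* They carry no duration or marrow data. The only combination data in 2.7 are 4 patients at 400 mg twice daily with no DLTs, too few and at too low a dose to settle the matter.

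**Conclusion.** The point holds as a defect in the formal rules, not as an absence of safety oversight. For Phase II, a literal reading of 8.1.3 leaves out a toxicity that the plan itself calls dose-limiting. For the RP2D, the sections disagree on whether a later event counts, and the decision may precede day 42 for the last patients enrolled.

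The size of the effect is unknown. Under the assumptions above, the RP2D decision is the main exposure: with half the events newly counted, the pass probability falls from 0.89 to between 0.84 and 0.68, while Phase II stopping rises from 0.003 to between 0.006 and 0.033. The upper-bound row is the least credible, because it supposes that no event is screened out as persistent MDS after one cycle. If aplasia is rare or mostly screened out, the effect is small. The plan should be changed because it does not implement its own definition and the correction is cheap.

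**What to change.** State in 4.1.1, 8.1.1 and 8.1.3:

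> A hematologic DLT whose cytopenia begins in cycle 1 counts as a first-cycle DLT when it meets the 6-week criterion at day 42 from C1D1. A patient without a DLT at day 28 who has ongoing Grade 3 or higher neutropenia or thrombocytopenia not back to baseline is pending for the six-patient decision and the Phase II looks until recovery, a non-hypocellular C2D1 marrow, or day 42. If cycle 2 has been started before day 42, the treating investigator and Medical Monitor decide attribution to cycle 1 from the counts and marrow before cycle 2 dosing.

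The last sentence keeps cytopenia caused by cycle 2 azacitidine from being charged to cycle 1. The return-to-baseline test follows 4.5 and keeps patients who entered with low counts from all being pending.

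In 8.2.2, add that a patient whose cycle 1 doses were held for such cytopenia is not replaced until that status is resolved. As an optional clarification, reword the clause on underlying MDS to say that the cytopenia is not explained by persistent or progressive MDS in the marrow.

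Cost: a delay of up to 42 − 28 = 14 days in the six-patient decision when a late-enrolled patient is pending, a similar wait at some Phase II looks, and a blood count near day 42 for pending patients only. Some disease-related cytopenias may be counted.
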